6.8.3 Biomarkers of infection (led by [name])

Investigation of aseptic or lymphocytic meningitis using conventional techniques often results in no pathogen being identified (5, 27). This can prevent patients receiving prompt appropriate medical management and may lead to poor utilisation of drugs, i.e. antibiotics and aciclovir. Thus there is a need to improve diagnostics.

We aim to use a molecular approach to improve diagnosis via the detection of gene 'building-blocks' (transcripts) generated by the patient during acute illness.

These 'building blocks' are generated by the patient's immune cells in response to illness. Examining the patterns of these responses, called gene-expression profiling, can help characterise the underlying immune process and the insult causing it. We will employ gene-expression profiling methods, already used by our group(28-30), to examine the patients' gene-expression responses (in blood and cerebral spinal fluid (CSF)) between different classes of central nervous system (CNS) infection (e.g. viral or bacterial meningitis) or the pathogen causing it (e.g. Herpes Simplex virus (HSV) or Enteroviruses). Because the host gene-expression profile reflects the reaction of immune cells in response to infection, we will also collect leukocytes, key immune cells, from the blood and CSF to help understand which immune cells are involved in generating the host response patterns.

We will collect samples on all patients with suspected meningitis. Utilising patients that are later confirmed to have a definite diagnosis (i.e. a pathogen is detected), we will examine gene-expression responses between these patients to identify gene-expression patterns that delineate between different classes of CNS infection. Later, we will then use these gene-expression signatures to differentiate classes of CNS infection where no pathogen is recovered.

The blood and CSF samples will be collected in PAXgene™ tubes (to be supplied by BIUK). These tubes stabilise the transcripts when out of the body. The samples will be collected at the time of routine venepuncture and LP (where the patient is recruited prior to LP). Leukocytes from venepuncture will be collected into CELL PREPARATION TUBES (2x8mls) Leukocytes from CSF will be collected into LiHeparin tubes. These tubes facilitate separate of leucocytes from the rest of the biological samples (<http://www.bd.com/vacutainer/products/molecular>).

Amendment AM08

Interim analysis has shown that the samples are being collected several days after admission (median 3 days). Due to prompt and correct usage of antibiotics, the information we will be able to gather from these samples will not help us in our aim of differentiating acute viral meningitis from acute bacterial or indeed meningitis from non meningitic illnesses. In order to try and improve this we will obtain samples as close to admission as possible. Preferably, with the admission bloods/lumbar puncture (LP). Due to the emergency nature of suspected meningitis bloods/CSF may be taken for RNA analysis at the same time as the routine bloods/LP (BUT NOT PROCESSED) without written informed consent. Informed consent will be deferred until the patient is more stable and settled in hospital. If consent is not given the samples taken will be DESTROYED.

The patient information leaflet will reflect the fact that samples may have already been taken and the consent form will also include an optional section on consenting to use samples already taken specifically for research purposes.

Key Questions

Can analysis of the human host response (examining RNA transcripts) during acute infection be used to help differentiate between different types of CNS infection (e.g. viral or bacterial meningitis)?

Can analysis of the human host response (examining RNA transcripts) during acute infection be used to help differentiate between different types of CNS pathogen causing meningitis (e.g. HSV or enterovirus meningitis)?

Statistical Analysis

This sample-size estimation utilises the model described specifically for micro-arrays by the Department of Bioinformatics and Computational Biology, MDAnderson Cancer Centre, University of Texas (<http://bioinformatics.mdanderson.org/MicroarraySampleSize>). The model assumes that on the log scale the expression of each gene is normally distributed and that measurement of each gene is independent of the next.

Pilot data used to inform the current sample size calculation: We have previously undertaken a pilot gene-expression study among patients with two types of neuro-infection (Tuberculous and bacterial meningitis; 18 and 16 patients respectively in each group). The study identified over 200 highly discriminatory transcripts with > 2 fold differential transcript abundance between the two groups. Individually re-testing a sub-set of the transcripts (n=20) identified on the arrays via RT-PCR the differences in transcript abundance between infection classes were confirmed. The mean standard deviation in gene-expression (across both groups) was 0.72 in the study ([name]. unpublished data).

The sample size needed to identify a 2x fold change in gene-expression between the two patient groups, accepting an average standard deviation in gene-expression of 0.72, a 5% false detection rate (i.e. a per-gene significance level alpha of 0.05) and 80% power, will be 9 (in each arm).

In another study that collected research samples during clinical indicated venepuncture being undertaken by our group in Nepal, more than 90% of those patients approached consented to participate in the study. Previous clinical studies undertaken on the infectious diseases wards in Royal Liverpool University Hospital (e.g. PIVOT, genetic susceptibility to *C. difficile* infection) have demonstrated a similar high willingness to participate (80-90%). Taking a conservative estimate that 20% participants may not consent then we will still recruit sufficient participants. Additional patients will be used towards developing a validation set of patients.

Sample collection

Two blood samples will be taken during admission one on recruitment and one 3-5 days later (or at discharge if this occurs sooner). These will be taken, where possible at the same time as routine venepuncture. If possible two further samples will be taken during convalescence; one at three months and one at 12 months. This will only happen if the patient is being followed up and will need to be assessed on a case by case basis. The blood samples will be 18.5 ml in total; 2.5ml will be collected into PAXGENE for RNA extraction, and the rest will be collected into heparin for leukocyte separation.

If a patient is enrolled in the study prior to having a lumbar puncture an extra 4.5 ml of CSF will be collected whilst collecting the other clinically indicated samples. The LP will not be carried out purely for research reasons. LP samples will be collected into RNA stabilisation and leukocyte separation medium. The study team will also be able to collect left over samples taken for clinical reasons, for example serum or CSF. This will only be done if the samples are surplus to clinical requirements. Convalescent blood samples will only be collected in patients followed up by the physician.

Sample processing

	Biological Fluid	Tube/Purpose	Volume	When			
				Recruitment	d3-5	3/12	12/12
In sites that can either process and	Peripheral Blood	1x PAXgene RNA tube	2.5mls	X	X	X	X
		2x CPT tube	16 mls	X	X	X	X

store leukocytes or transfer them to another site that can within 8 hours	CSF	1xPaxgene RNA tube	2.5mls	X			
		Lithium Heparin	2 mls	X			
In sites that can't process leukocytes or transfer samples within 8 hours.	Peripheral Blood	1x PAXgene RNA tube	2.5mls	X	X	X	X
	CSF	1xPaxgene RNA tube	2.5mls	X			

All tubes utilized will be compatible with blood and CSF collection systems currently in use within the hospital(s).

RNA: Venous blood or CSF will be collected into PAXGENE tubes (2.5mls). Samples will be stored at room temperature for 2 hours then stored at -70c in open racks (to avoid differential freezing). Total RNA will be extracted in sample batches following the manufacturer's protocol.

Leukocytes: Leukocytes from venepuncture will be collected into CELL PREPARATION TUBES (CPT) (2x8mls). These tubes facilitate separate of mononuclear leucocytes from erythrocytes and plasma. Leukocytes from CSF will be collected into LiHeparin tubes. The samples will be processed within 8 hrs of collection. Separated leukocytes will have a cryo-protectant added (DMSO) and then be stored. Leucocyte samples will only be collected where research personnel are available to support leucocyte processing and storage or where a site is able to get them to another site that can within the 8 hours. All samples will be stored in -80°C freezers. All storage of material containing cells will be fully compliant with the human tissue act (HTA).

This substudy will be funded by FSF funding from the Liverpool Biomedical Research Centre.

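### The gene-expression sample size of 9 per arm rests on a wrong equation of a 5% false detection rate with a per-gene alpha of 0.05

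*Protocol*

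**What the plan says.** The statistical analysis part of Protocol section 6.8.3 describes its method thus: "This sample-size estimation utilises the model described specifically for micro-arrays". Its stated assumptions are that "on the log scale the expression of each gene is normally distributed and that measurement of each gene is independent of the next".

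The target is set out as "The sample size needed to identify a 2x fold change in gene-expression between the two patient groups". The SD is put at 0.72. The error rate, power and resulting size are then given together: "a 5% false detection rate (i.e. a per-gene significance level alpha of 0.05) and 80% power, will be 9 (in each arm").

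The SD comes from a pilot in tuberculous and bacterial meningitis (18 and 16 patients). Of that pilot the section reports: "The study identified over 200 highly discriminatory transcripts with > 2 fold differential transcript abundance between the two groups".

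The section then allows for 20% of participants not consenting, concludes that recruitment will still be sufficient, and directs additional patients to a validation set. It gives no number of transcripts to be tested, no expected share that truly differ, and no per-gene threshold stricter than 0.05.

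**The concern.** A per-gene alpha is the probability that an unchanged gene is flagged. A false detection rate, in the usual array sense, is the share of flagged genes that are unchanged. The sentence joins them with an i.e., as if fixing one fixed the other. When thousands of genes are tested and few change, 5% of the unchanged ones can outnumber all the true detections.

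Two things hang on this. First, 9 per arm is the benchmark for calling recruitment sufficient and for releasing further patients to validation, so too low a figure could close the discovery set early. Second, section 6.8.3 intends the resulting signatures to classify patients in whom no pathogen is recovered, where there is no microbiological reference to expose a poor signature.

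**Working it through.** **Inputs from section 6.8.3.** Fold change 2, SD 0.72 on a log scale, alpha 0.05, power 80%, equal arms.

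**Assumptions of this check.** Log base 2, so that a 2-fold change is a difference of 1. The protocol says only that the scale is logarithmic, but base 2 reproduces its figure, whereas natural logs would give 17. Tests are two-sided. The share of truly changed genes, p, is not in the protocol and is varied from 1% to 10%.

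**Step 1: reproduce 9.** Normal approximation:

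n = 2 × (1.960 + 0.842)² × 0.72² / 1² = 8.14, rounded up to 9.

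The t-test needs 10 per arm; its power at 9 is 0.79. So the stated figure is arithmetically right for one gene at an unadjusted alpha of 0.05. No multiplicity term enters.

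**Step 2: false share among detections at alpha 0.05.** With 80% power:

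false share = 0.05(1 − p) / [0.05(1 − p) + 0.80p].

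For p = 1%: 0.0495 / (0.0495 + 0.008) = 86%. For p = 10%: 0.045 / (0.045 + 0.08) = 36%.

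As counts, if 200 of an assumed 20,000 transcripts change: 0.05 × 19,800 = 990 false against 0.80 × 200 = 160 true, and 990/1,150 = 86%.

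Setting the false share to 5% and solving gives p = 0.05 × 0.95 / (0.05 × 0.95 + 0.80 × 0.05) = 0.0475/0.0875 = 54%. The equivalence therefore holds only if about 54% of all genes truly change.

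**Step 3: size for a true 5% rate at 80% power.** The per-gene alpha required is

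alpha = (0.05/0.95) × 0.80 × p/(1 − p).

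The sample size and the power at 9 per arm, for a gene at exactly 2-fold, follow by each method:

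| Share changed | False share at alpha 0.05 | Alpha needed | n per arm, normal | n per arm, t-test | Power at 9, normal | Power at 9, t-test |
|---|---|---|---|---|---|---|
| 10% | 36% | 0.0047 | 14 | 17 | 55% | 40% |
| 5% | 54% | 0.0022 | 16 | 19 | 45% | 30% |
| 2% | 75% | 0.00086 | 19 | 21 | 35% | 19% |
| 1% | 86% | 0.00043 | 20 | 23 | 28% | 13% |

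Like should be compared with like: the protocol's 9 becomes 14 to 20 by the normal approximation, and the t-test's 10 becomes 17 to 23.

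**Step 4: patients available.** Section 7.2 expects 160 bacterial, 58 enterovirus and 38 HSV-2 cases. After the protocol's 20% non-consent these are 128, 46 and 30, all above 23.

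**The case against.** The strongest reply is about wording. The text says detection, not discovery, and at once defines the term as a per-gene alpha. Read that way, the sentence agrees with itself and 9 is correct. That much stands: the arithmetic is not at fault, and the protocol does not explicitly promise array-wide FDR control. But a rate of false detections, in a calculation described as specific to micro-arrays, is naturally read as a rate among detections. On the narrow reading, the sample size simply carries no control across the array. Either way the sentence needs correcting.

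Four stronger inferences are tempting but not supported.

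- A reader might infer that the gene list will be mostly false. Section 6.8.3 states no rule of selecting at raw p < 0.05. Multiplicity correction may be in an analysis plan not seen here, and a validation set is foreseen.
- A reader might take about 23 per arm as the right number, or conclude that 9 has almost no power. The 23 and 13% are t-test results at the 1% end of an assumed range, and setting them beside a normal-approximation 9 inflates the gap. The pilot's 200 transcripts are a highly discriminating subset from a different contrast, not an estimate of all changed genes. Larger changes are also easier to find: at the 1% threshold, t-test power at 9 is about 60% for a 3-fold and 89% for a 4-fold change.
- A reader might conclude that VZV must be made exploratory. Section 6.8.3 names HSV and enterovirus as its pathogen examples, not VZV. The 18 VZV cases in section 7.2 come from a one-year, 31-centre projection, whereas the Protocol Summary gives 35-45 sites and an extension to 5 years.
- A reader might conclude that recruitment is inadequate. Section 7.2 points the other way for the main contrasts. It counts expected cases rather than usable RNA samples, however. Section 6.8.3 reports that samples were being collected a median of 3 days after admission, and extra research CSF requires enrolment before lumbar puncture.

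**Conclusion.** The point holds as a wrong stated basis for a sample size. Nine per arm is a single-gene, unadjusted figure and does not carry a 5% rate of false detections unless about 54% of genes truly change, which nothing in the protocol suggests. If 1% to 10% change, a true 5% rate at 80% power needs roughly one and a half to two and a half times as many per arm. This rests on log base 2, two-sided tests, the common SD of 0.72, genes at exactly 2-fold, and the assumed share changed. The size of the shortfall is therefore a range, not one number. Severity is moderate: this is a discovery sub-study, and the study's primary objective, the prevalence of viral meningitis, is untouched.

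**What to change.** In section 6.8.3:

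- Delete the i.e. that equates the two error rates.
- State that 9 per arm applies to one gene at an unadjusted two-sided alpha of 0.05, and name the log base and the test.
- Add an FDR-based size as a range, with the assumed number of transcripts and share changed. On the assumptions above it is 14 to 20 per arm (normal approximation) or 17 to 23 (t-test).
- State that the discovery analysis controls FDR.
- Assign patients to discovery up to that size before the rest go to the validation set.

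The cost is a revised paragraph and a recomputed figure. No extra recruitment is expected for the main contrasts, but the number of usable RNA samples in each class should be checked before the discovery set is closed.

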6.8.4 Proteomics

In addition to the genomics work we will also build on the proteomics work that our group are already involved in.

Previous studies have demonstrated the power of linking protein and RNA expression methodology (31). Known proteins predicted to be differentially regulated by the transcriptomic studies can be measured, if secreted, in the corresponding plasma using ELISA or cytokine bead array (CBA) approaches (the latter allows us to screen for large number of target proteins in a relatively small volume of sample). Where antibodies to the protein are not available we may also consider 'tagging' target proteins and undertake quantification of the tagged proteins via Mass spectrometry.

In addition, in a selective sub-group of patients we will utilise SELDI mass spectrometry profiling, which enables rapid proteomic assessment of all protein peaks. Peaks of interest in particular diagnostic groups will be identified with the aid of dedicated software. The putative identification of peaks will be made by interrogating the publicly available databases with molecular masses of interest using tools available at www.expasy.ch (TagIdent, Findmod, Findpept) and/or Protein Prospector (<http://prospector.ucsf.edu/>)

Using these techniques we can compare the proteomic profiles of different groups of patients, such as

- those with viral meningitis with good outcomes,
- those with poorer outcomes and
- controls.

Our group are already collaborating with the University of Manchester, Liverpool School of Tropical Medicine and UCH in London where these techniques are already being used. [name] (a co-applicant in this study) has extensive experience of these techniques.

Much of the work done previously on protein expression in viral meningitis has been done on viral meningitis as a group. We will be able to separate out the different causes of viral meningitis and compare between viruses as well as with our non-meningitic controls and others with undiagnosed causes of aseptic meningitis.

An extra sample of blood will be taken for this work; again this can be taken at the same time as routine venepuncture.

The CSF for the proteomics will be obtained from any leftover CSF.

6.8.5 DNA Sampling (led by [name])

6.8.5.1 Background

All individuals are naturally exposed to range of viruses and bacteria during their life. However, in some the pathogen exposure can lead to devastating infection within the central nervous system. Infections are controlled by the body's immune system. The success of the immune response in preventing development of infection is influenced by inheritable factors of resistance and predisposition in the patient (genetic background of the patient) and the pathogen (genetic background of the pathogen).

These inheritable factors are based on DNA. DNA is the basic "instruction book" for the cells that make up our bodies and other living organisms including bacteria and some viruses. The DNA of a person is more than 99% the same as the DNA of any other unrelated person. But no two people have exactly the same DNA except identical twins. Differences in DNA are called genetic variations. These variations explain some of the physical differences, e.g. shape of your nose, among people, and partly explain why some people get diseases, e.g. meningitis while others do not.

Sometimes these variations have been shown to predispose to a variety of related, but different diseases(32).

We want to examine these factors in patients who are diagnosed with aseptic meningitis compared to individuals who haven't suffered meningitis or suffered less severe meningitis.

Control human sequences will be obtained from global and UK DNA data-bases (e.g. Wellcome Trust Case Control Consortium; MRC UK Biobank). Pathogen sequence data will be compared between samples from different body sites e.g. cerebral spinal fluid and genital lesions or from patients' with less severe brain infection.

Better understanding of these inheritable factors will help the design of new treatments against brain infections in the future.

6.8.5.2 Key Objectives

- To identify differences in the frequency of polymorphisms in human DNA sequences among patients with confirmed CNS infections compared to controls.
- To identify differences in the frequency of polymorphisms in pathogen recovered from cerebrospinal fluid compared to blood and/or genital lesions among patients with confirmed CNS infection.

6.8.5.3 Patient recruitment

All patients will be given the option of consenting to this part of the study. If they do not wish to have their DNA sampled they can still be part of the main study. Anybody who meets the eligibility criteria can consent to DNA sampling.

6.8.5.4 Statistical analysis

Human DNA study.

The initial study will look at genetic risk associated with the syndrome of aseptic meningitis. Based on the sample size calculation in section 7.2 we expect in excess of 220 patients with aseptic meningitis.

The sample size calculation assumes marker allele is the same as the disease allele, marker allele is present in 10% of the population and has 100% penetrance ($D'=1$). It also assumes there will be 1:4 ratio of cases to controls, a study power 80% and significance 95%. Controls will be obtained from the Wellcome Trust Case Control Consortium (containing a bank of up to 4500 DNA sample from control subjects).

Based on genotype relative risk of between 2.25 and a multiplicative genotypic risk model, the study will require 218 patients diagnosed with aseptic. Sample size estimation utilised the genetic power calculator (<http://pngu.mgh.harvard.edu/~purcell/gpc>).

Pilot Pathogen DNA study

Currently, the largest study of HSV sequence diversity in clinical samples looked at 28 patients and only examined selected regions of the viral genome (33). Based on advances in genome sequencing we are now able to sequence the whole-genome which may identify new areas of sequence diversity in the Herpes Simplex virus (34). We therefore intend to undertake a pilot study sequencing whole-genome pathogen DNA in the collected samples and use the resulting levels of sequence diversity to estimate the sample size required to do a full study.

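### The human DNA sub-study's 218 cases does not follow from the inputs the protocol states for it, and the effect size among those inputs is incomplete

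*Protocol*

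**What the plan says.** Section 6.8.5.4 (Human DNA study) takes the marker allele to be the disease allele, puts its presence in the population at 10%, and describes it as having 100% penetrance, with D'=1 in brackets. It continues: "It also assumes there will be 1:4 ratio of cases to controls, a study power 80% and significance 95" (per cent). The effect size reads "Based on genotype relative risk of between 2.25 and a multiplicative genotypic risk model", with no second bound. The conclusion is that "the study will require 218 patients diagnosed with aseptic" meningitis, obtained from an online genetic power calculator. Sidedness, disease prevalence and the number of variants to be tested are not given.

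For feasibility the same section relies on section 7.2: "we expect in excess of 220 patients with aseptic meningitis". The table in section 7.2 shows 223. Section 6.8.5.3 makes DNA sampling optional, and no DNA consent rate is given. The only planning figure for refusal is in the biomarker sub-study, section 6.8.3: "Taking a conservative estimate that 20% participants may not consent".

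**The concern.** A sample size should be recoverable from its stated assumptions. Here a relative risk of 2.25 on a 10% allele, with four controls per case, is a large effect for a single test at 5%, and 218 cases looks several times too many. Either the significance level or the risk definition must differ from what is written.

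What is at stake is how the sub-study is read and reported. If the written 5% level and a per-allele risk of 2.25 are right, 218 is a large over-estimate. If 218 is right, the power claim depends on a threshold or risk definition that nobody can check, and recruitment has almost no slack against the forecast the section relies on. A reader cannot tell which case applies.

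**Working it through.** **Inputs (section 6.8.5.4).** Control allele frequency p = 0.10; marker is the disease allele, so no dilution; 4 controls per case; power 80%; alpha 5%; relative risk 2.25, multiplicative. Population (unscreened) controls are assumed unless stated otherwise.

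**The forecast reproduces.** Section 7.2 scales 18 aseptic cases in 3 months at 10 hospitals to one year and 31 centres: 18 × 4 × 3.1 = 223.2, matching its 223.

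**The 218 does not.** Under a multiplicative model with risk R per allele, the case allele frequency is p1 = pR / (pR + 1 − p). A 1-df allelic test on two alleles per person, using the pooled-variance (noncentrality) form, needs

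n cases = (z_alpha + z_power)² × p̄(1 − p̄) × 1.25 / (2d²), with p̄ = (p1 + 4p)/5 and d = p1 − p.

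*Reading A: 2.25 is the risk per allele.*
- p1 = 0.225 / 1.125 = 0.20; d = 0.10; p̄ = 0.12; p̄(1 − p̄) = 0.1056.
- Multiplier: 0.1056 × 1.25 / (2 × 0.01) = 6.60.
- Two-sided 5%: (1.960 + 0.842)² = 7.849, so n = 51.8, that is 52. The Fleiss formula gives 57.4, that is 58.
- One-sided 5%: 40.8 (Fleiss 45.8).
- Power with 218 cases at two-sided 5%: above 99.9% by either formula.
- At this allele frequency, a continuity correction or a 2-df genotypic test raises the two-sided requirement only to about 64. Reading 10% as a carrier frequency raises the maximum to about 111.

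*Reading B: 2.25 is the homozygote risk, so 1.5 per allele (1.5² = 2.25).*
- p1 = 0.15 / 1.05 = 0.1429; d = 0.0429; p̄ = 0.1086; multiplier 32.93.
- Two-sided 5%: 7.849 × 32.93 = 258.5 (Fleiss 273.4). Power with 218: 73% (Fleiss 71%).

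Neither reading gives 218 at two-sided 5% with 80% power.

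**What would give it.** Each route needs an assumption the text does not state.

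| Risk per allele | Alpha | Noncentrality n | Fleiss n |
|---|---|---|---|
| 2.25 | 1e-6, two-sided | 216.9 | 228.3 |
| 1.5 | 5%, one-sided | 203.6 | 216.9 |

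A third route is 1.5 per allele at two-sided 5% with controls screened free of disease and an assumed 10% prevalence. The control frequency becomes (0.10 − 0.10 × 0.1429)/0.90 = 0.0952, and Fleiss gives about 217.

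**The penetrance label.** D'=1 means complete linkage disequilibrium between marker and disease allele. Penetrance is the probability of disease given genotype. If every carrier were affected, a second copy could not raise the risk, which contradicts the multiplicative model. The label is wrong, but D'=1 shows the intended input and no number above changes.

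**Margin.** 218/223 = 97.8%. On the 223 forecast, 90% DNA consent gives 0.9 × 223 = 201 cases and 80% gives 0.8 × 223 = 178. Power at those numbers depends on which inputs are true:

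| Inputs | 201 cases | 178 cases |
|---|---|---|
| 2.25 per allele, 5% two-sided | >99% | >99% |
| 2.25 per allele, 1e-6 two-sided | 70–73% | 60–62% |
| 1.5 per allele, 5% one-sided | 77–80% | 73–75% |

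**The case against.** The strongest reply is that the effect-size phrase is incomplete, so the text does not define a single calculation and 52 cannot be called its answer. That stands in part: 52 to 58 belongs to one reading. But the other natural reading misses 218 in the opposite direction, so an incomplete phrase does not rescue the figure.

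A reader might infer that the calculation was really run at alpha 1e-6. The documents do not support that. No such level and no variant count appears, and a one-sided 5% test at 1.5 per allele fits about as well. Choosing an alpha because it returns 218 would be fitting the assumption to the answer.

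A reader might also infer that consent leaves only 178 cases. That is not established either. The 20% refusal belongs to a different sub-study and is called conservative there, beside observed participation of 80–90% and above 90%. The 223 is a one-year, 31-centre forecast that section 7.2 calls a likely underestimate, alongside up to 356 viral or aseptic cases a year from hospital statistics (80% of 356 is 285). The protocol summary now gives 35–45 sites and an extension from 2 to 5 years. The shortfall also disappears if about 52 cases are enough.

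Nor does the text say that many variants will be tested at 5%. It describes a single-marker calculation, and multiplicity handling may properly sit in an analysis plan that is not at hand.

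Finally, the sub-study is optional and feeds no primary or listed secondary outcome in section 7.1. That limits the weight of the point, not its correctness.

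**Conclusion.** The point holds in this form: 218 cases cannot be derived from the inputs in section 6.8.5.4. At two-sided 5%, the requirement is about 52 to 58 cases if 2.25 is the risk per allele, or about 258 to 273 if it is the homozygote risk. The power of 218 cases is then over 99.9% or 71–73% respectively, against the stated 80%. These figures assume an allelic test, a 10% allele frequency and unscreened population controls. At least one material input is therefore missing or misstated, and the documents do not show which.

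Two wording faults sit in the same passage: the one-ended risk range, which is substantive, and the penetrance label, which is editorial.

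On feasibility, the supportable claim is narrow. The section compares 218 with a forecast just above 220 and makes no allowance for optional DNA consent. That matters only if the true requirement is near 218. It should be corrected, as a matter for this sub-study alone.

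**What to change.** In section 6.8.5.4:

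1. Give the heterozygote and homozygote relative risks as single values, or both ends of the range with the value used for sizing.
2. State the sidedness, the disease prevalence entered in the calculator, and the alpha actually used. If that alpha is corrected for multiplicity, give the number of variants it covers.
3. Replace the penetrance wording with complete linkage disequilibrium (D'=1), and say whether 10% is an allele or a carrier frequency.
4. Rerun the calculation and restate the required number of cases, or the power at 218.
5. If the requirement is still near 218, compare it with a recruitment forecast for the study as extended, apply an explicit DNA consent rate, and restate the power or detectable relative risk at the resulting number.

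The cost is a few lines of text and one recalculation, with no change to recruitment or sampling procedures. Depending on which inputs prove correct, the stated power may become less favourable.
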